shock process. Administration of aldosterone in mice resulted in improved response to phenylephrine⁶. Based on the RCTs performed in human subjects, however, it is controversial whether addition of fludrocortisone provides any true benefit in refractory septic shock patients. Moreover, to date there has not been a trial, whether retrospective or prospective, that has directly compared the use of hydrocortisone alone versus the combination of hydrocortisone and fludrocortisone. Because of this lack of data, we will be investigating the use of hydrocortisone alone versus the combination in critically ill septic shock patients admitted to the medical intensive care unit. Currently, both are considered standard of care both within and outside of the University of Tennessee Medical Center Knoxville.

Objective: To determine if the use of hydrocortisone plus fludrocortisone is associated with a faster resolution of shock (defined as 24 hours vasopressor free) when compared to the use of hydrocortisone alone in medical, critically ill septic shock patients

Study Design and Methods:

This study is a single-center, prospective, open-label, randomized trial which will evaluate adult patients admitted with septic shock to the medical critical care unit (MCC).

Inclusion Criteria:

- Age \geq 18
- Critically ill medicine patients requiring addition of stress dose steroid therapy (hydrocortisone) in addition to pressors for septic shock management during their ICU stay
- Fludrocortisone administered within 24 hours after initiation of hydrocortisone if in combination therapy group

Exclusion Criteria:

- Use of fludrocortisone and/or hydrocortisone for any reason other than septic shock management during ICU stay
- Fludrocortisone/hydrocortisone initiated by any service other than critical care medicine
- Prior use of fludrocortisone/hydrocortisone at time of admission (home or outside facility)
- Patients not appropriate for study inclusion as determined by provider discretion
- Patients receiving steroid therapy not in accordance with assigned group per location (MCC1 or MCC2)
- Patients re-admitted to the MCC during the same admission and restarted on vasopressor therapy will be noted during data collection and only the initial admission will be included for analysis
- Any patient receiving greater than one dose of hydrocortisone 100 mg
- Physical or medical contraindication to receiving PO or PER FT (per feeding tube) fludrocortisone.

Protocol:

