All patients admitted to the medical critical care unit side 1 (MCC1) or side 2 (MCC2) will be provided a “Notice of Research.” At any time, refusal or withdrawal from the study can be requested by the patient, patient advocate, or provider.

Patients that meet inclusion criteria for the study will receive either hydrocortisone 50 mg IV Q6h alone or a combination of hydrocortisone 50 mg IV Q6h plus fludrocortisone 50 mcg PO/PER FT daily. Fludrocortisone must be initiated and administered within 24 hours after the first administered dose of hydrocortisone. Because fludrocortisone is only available as a 100 mcg tablet, the nurse at the bedside will split the tablet into two as to provide a 50 mcg dose. This is standard of practice currently when fludrocortisone is utilized in our institution.

Steroid therapy assignments will be randomized based on patient location. For three consecutive months starting in October 2018, all patients in MCC1 will receive hydrocortisone alone and all patients admitted to MCC2 will receive hydrocortisone plus fludrocortisone. Then, in the following three consecutive months, this will be flipped and MCC1 will receive hydrocortisone plus fludrocortisone while MCC2 will receive hydrocortisone alone. This change in group assignments will occur to account for the difference in number of beds between MCC1 and MCC2, and to minimize the potential differences in patient acuity by location.

Initiation of hydrocortisone for inclusion in the study will be determined solely by provider discretion as the standard of care for septic shock patients. Once hydrocortisone is initiated, fludrocortisone will be initiated within 24 hours for patients on the qualifying side of the unit, unless any of the previously stated exclusion criteria are present. Because these interventions are currently utilized and considered standard of care in the MCC, data collection will be performed retrospectively by generating a list of patients in the MCC receiving hydrocortisone therapy.

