 - Reinitiation of vasopressor therapy (after vasopressor free for 24 hours)
 - Reinitiation of hydrocortisone and/or fludrocortisone
 - Mechanical ventilator free days during ICU admission
 - Duration of steroid therapy
- Safety Endpoints
 - Documentation of two consecutive point of care blood glucose checks >180 mg/dl after initiation of hydrocortisone and/or hydrocortisone/fludrocortisone
 - Gastrointestinal bleed during study period (as documented by provider)
 - Severity of bleed as determined by GUSTO criteria
 - Severe: deadly bleeding; intracerebral bleeding or substantial hemodynamic compromise
 - Moderate: bleeding requiring transfusion
 - Mild: other bleeding not requiring transfusion or causing hemodynamic compromise
 - New initiation of renal replacement therapy during study period
 - Electrolyte abnormalities
 - Sodium level greater than 150 mEq/L during study period
 - Potassium level greater than 5.5 mEq/L during study period

Other Data Collected:

- Demographics: Age, sex, weight, height, BMI, ethnicity (race)
- Septic Shock Bundle initiated
- WBC at time of steroid initiation and at discontinuation

- Initial lactic acid level on admission
- Lactic acid level at initiation of vasopressors
- Vasopressor initiated (norepinephrine, epinephrine, phenylephrine, vasopressin, dopamine, dobutamine)
- Vasopressor dose when steroid therapy was initiated (mcg/min and mcg/kg/min)
- Max vasopressor dose during study period
- SOFA Score
- APACHE Score
- Charlson Comorbidity Index
- Site of infection (lung, intraabdominal, urogenital, skin, CNS, endocarditis, bacteremia, unknown, etc.)
- Non-contaminant, positive culture during study period with clinical correlation to septic shock event
 - Site of culture
 - Gram Positive
 - Gram Negative
 - Viral
 - Fungal
 - Organism
- Comorbidities:
 - Documented heart failure
 - Documented chronic kidney disease stage III-IV not requiring renal replacement therapy at baseline
- Documentation of concurrent cardiogenic shock during study period
- Serum creatinine at initiation of steroid therapy
- Serum creatinine at discontinuation of steroid therapy
- Renal replacement therapy at the initiation of steroid therapy
- Mechanical ventilation at initiation of steroid therapy
- Other systemic steroid use (methylprednisolone, dexamethasone, prednisone) prior to pressor initiation
- Systemic steroid use prior to admission (home medication)

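### The exclusion for more than one 100 mg hydrocortisone dose has no time window, so it can remove correctly assigned patients because of dosing after open-label assignment

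*Combined protocol and SAP*

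**What the plan says.** All references are to the combined protocol and SAP.

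- **Exclusion Criteria.** One criterion reads "Any patient receiving greater than one dose of hydrocortisone 100 mg". It does not say over what period doses are counted. For patients readmitted to the unit, a neighbouring criterion says that "only the initial admission will be included for analysis".
- **Protocol section, regimen.** Patients "will receive either hydrocortisone 50 mg IV Q6h alone" or the same hydrocortisone schedule with fludrocortisone. No 100 mg or loading dose is described. The start of hydrocortisone is left to the provider.
- **Protocol section, assignment and identification.** The arm follows from the side of the unit and the calendar period. Then "data collection will be performed retrospectively by generating a list of patients in the MCC receiving hydrocortisone therapy". The same section has fludrocortisone started within 24 hours unless an exclusion criterion is present.
- **Outcomes.** The primary endpoint is time to 24 hours free of vasopressors. Secondary endpoints include mortality at several times, restart of vasopressors once the patient has been free of them for 24 hours, and "Reinitiation of hydrocortisone and/or fludrocortisone", the last with no dose or time limit.
- **Other Data Collected.** Individual 100 mg hydrocortisone doses are not on the list.
- **Statistical Power and Statistical methods.** The target is 39 per group, with no stated allowance for exclusions. No analysis population is defined.

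**The concern.** A second 100 mg dose is a treatment decision that can fall days after the arm is fixed and known. The provider may give it because shock is not resolving or has come back, and may be influenced by the arm. Excluding on that decision makes membership of the analysis set depend on something that happens after assignment. The two groups compared are then no longer the two groups assigned.

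This differs from the exclusion for therapy that does not match the assigned side. Here a patient who received exactly the assigned arm can be dropped.

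At stake are the primary endpoint and mortality, if the dropped patients differ in prognosis and the arms lose different shares of them. The steroid reinitiation endpoint is also exposed: a patient given one 100 mg dose at the start and another at a restart has the event and is excluded because of it. Since 100 mg doses are not a listed data item, the effect of the rule could not readily be examined later.

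**Working it through.** **1. What the rule catches, case by case**

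| Course | 100 mg doses | Excluded? | Steroid reinitiation event? |
|---|---|---|---|
| Restart at the stated 50 mg schedule | none, or one earlier | no | yes |
| One 100 mg dose at restart, none earlier | 1 | no | yes |
| One 100 mg dose early, another at restart | 2 | yes | yes |
| Two or more 100 mg doses during continuing therapy | 2 or more | yes | no |

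Only the third row loses a reinitiation event. The fourth row bears on time to shock resolution and mortality.

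**2. The plan's sample size.** Inputs from Statistical Power: means 96 and 72 h, SD 36 h, two-sided alpha 0.05, 1:1 allocation. No power figure is stated; 80% is assumed here.
- d = (96 − 72)/36 = 0.667.
- The t-test needs 36.3, so 37 per arm. With the Mann-Whitney efficiency 3/π = 0.955, 36.3/0.955 = 38.02, so 39. The stated figure is reproduced.
- t-test power at 39 per arm is 0.83.

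**3. Loss of patients** (excluded share assumed, and 78 assumed to be counted before exclusion)

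| Excluded | Left per arm, 39(1 − f) | t-test power | Needed per arm, 39/(1 − f) |
|---|---|---|---|
| 5% | 37.0 | 0.81 | 42 |
| 10% | 35.1 | 0.79 | 44 |
| 15% | 33.1 | 0.76 | 46 |
| 20% | 31.2 | 0.74 | 49 |

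**4. Reinitiation rate.** Assume a true rate of 15%, a share f of those patients removed, and nobody else removed. Observed rate = 0.15(1 − f)/(1 − 0.15f).
- f = 0.25: 0.1125/0.9625 = 11.7%
- f = 0.50: 0.075/0.925 = 8.1%
- f = 0.75: 0.0375/0.8875 = 4.2%

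**5. Primary endpoint.** Assume that removed patients resolve 60 h later than the rest of their arm, with 10% removed in one arm and 5% in the other. Removal lowers the arm means by 0.10 × 60 = 6 h and 0.05 × 60 = 3 h, so the difference moves by 3 h, or 3/24 = one eighth of the planned effect.
- Slower arm loses 10%: (96 − 6) − (72 − 3) = 21 h, towards no difference.
- Faster arm loses 10%: (96 − 3) − (72 − 6) = 27 h, away from it.

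A less favourable bound: if only one arm (mean 96, SD 36, normal) lost 5% to 15% of its patients, its mean would fall by about 1.5 to 5 h if they came at random from the slower half, and by about 4 to 10 h if they were its slowest.

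**The case against.** The strongest reply is that the criterion is about entry. The Protocol section withholds fludrocortisone when an exclusion criterion is present, which suggests that criteria are checked around the hydrocortisone start. On that reading the rule tolerates one initial 100 mg dose and screens out higher-dose regimens. This reading is possible, but the text does not limit the rule to it: other criteria in the same list, such as off-assignment therapy and readmission, can only be known later, and patients are listed retrospectively. The fair description is a rule without a window, not one shown to count doses over the whole stay.

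Several stronger readings are tempting, and the documents do not support them.
- A reader might infer that the rule removes patients re-dosed for recurrent or worsening shock as such. It needs at least two 100 mg doses, and nothing says that restarts or deterioration are treated at 100 mg.
- A reader might count worsening shock as a lost reinitiation event. Vasopressor reinitiation requires 24 hours off first, and more hydrocortisone during continuing therapy is not a restart.
- A reader might infer that the slowest resolvers leave the primary analysis. A patient whose vasopressors are reinitiated under the plan's definition has already met the primary endpoint and need not be slow.
- A reader might see a flat contradiction with the regimen. It is an undescribed dose, which calls for reconciliation.

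It also stands that restarts after readmission to the unit appear to fall outside the analysis whatever this rule says. And a 3 h shift is modest: the standard error of the difference at 39 per arm is 36 × √(2/39) = 8.2 h, so 3 h is about 0.4 of it.

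**Conclusion.** The point holds in limited form. The criterion has no time window and is applied to patients found after the fact, so it permits selection on open-label, provider-chosen dosing after assignment. It can bias time to shock resolution and mortality, and it can delete some steroid reinitiation events. No analysis population in the plan keeps these patients in.

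The size is not known. The documents give no rate of repeated 100 mg dosing, no rate by arm and no outcome for such patients. Apart from the planned means, SD and sample size, every input to the bias and loss figures above is an assumption. The direction is open too: the same assumed shares move the difference to 21 h or to 27 h, depending on which arm loses more. The power figures apply only if 78 counts patients before exclusion; recruiting to 78 evaluable patients would restore power but not remove the bias. The change is worth making because it is cheap and removes the selection whatever its size.

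**What to change.** In the Exclusion Criteria and Statistical methods:

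1. State that no patient leaves the primary or secondary analyses because of 100 mg hydrocortisone doses given after assignment, and that such patients are analysed in their assigned group.
2. Add 100 mg hydrocortisone doses, with date and time, to Other Data Collected.
3. Apply the exclusion only in a sensitivity (per-protocol) analysis, and report the number affected by arm.

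A window tied to the hydrocortisone start would not do the same job. Assignment follows from location, so doses chosen at that start are also chosen with the arm known.

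Separately, the sponsor must reconcile the Exclusion Criteria, which implicitly tolerate one 100 mg dose, with the regimen in the Protocol section, which describes none.

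The cost is a few sentences, one data item and one sensitivity analysis. The downside is small: a few patients with higher hydrocortisone exposure stay in the main analysis.

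### The exclusion for a contraindication to enteral fludrocortisone covers both arms on paper, but the plan has no procedure or data field to apply it equally, so patients are likely to be removed mainly from the combination arm

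*Combined protocol and SAP*

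**What the plan says.** All places are in the combined protocol and SAP.

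- **Exclusion Criteria.** One item is "Physical or medical contraindication to receiving PO or PER FT (per feeding tube) fludrocortisone". It names no arm, although only one arm is due to receive the drug. Another excludes "Patients receiving steroid therapy not in accordance with assigned group per location (MCC1 or MCC2").
- **Inclusion Criteria.** One item applies to a single arm: "Fludrocortisone administered within 24 hours after initiation of hydrocortisone if in combination therapy group".
- **Protocol, allocation.** "Steroid therapy assignments will be randomized based on patient location". The unit sides swap after three months, and the trial is open label, so the arm is known before anyone judges eligibility.
- **Protocol, entry.** "Initiation of hydrocortisone for inclusion in the study will be determined solely by provider discretion". No enteral assessment is attached to this step.
- **Protocol, use of the exclusions.** Once hydrocortisone has started, "fludrocortisone will be initiated within 24 hours for patients on the qualifying side of the unit, unless any of the previously stated exclusion criteria are" found to apply. No matching step is described for the hydrocortisone-alone side.
- **Protocol, cohort.** "data collection will be performed retrospectively by generating a list of patients in the MCC receiving hydrocortisone therapy".
- **Outcomes and Other Data Collected.** The nearest items are "Site of infection (lung, intraabdominal, urogenital, skin, CNS, endocarditis, bacteremia, unknown, etc".), ventilation at steroid initiation and provider-documented gastrointestinal bleeding. None records enteral access, nil-by-mouth status, ileus or a contraindication to the tablet.

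The plan describes no intention-to-treat set, no screening log and no count of exclusions by arm.

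**The concern.** On the combination side, a contraindication comes to light because someone has to give an enteral tablet and cannot. On the hydrocortisone-alone side the study drug is intravenous, so nothing in the described workflow raises the question. Take two patients alike in every respect, neither with a usable enteral route. The one on the combination side meets this exclusion, fails the 24-hour inclusion criterion and counts as not treated per assigned side. The other receives hydrocortisone, appears on the list and is analysed unless an abstractor thinks to ask whether fludrocortisone would have been possible.

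The hydrocortisone-alone arm may therefore keep a subgroup that the combination arm loses. If those patients stay in shock longer, die more often or bleed more, the combination would look better with no drug effect. That would touch the primary endpoint, mortality and the gastrointestinal-bleed safety endpoint.

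The point needs its own remedy. Analysing all eligible patients by assigned side would undo the 24-hour and adherence rules, but the contraindication criterion would still define who is eligible.

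**Working it through.** **Step 1. The plan's own figure.** Statistical Power gives means of 96 h and 72 h, SD 36 h, two-sided alpha 0.05, 1:1 allocation and 39 per group (78 in total). Power is not given as a number; 80% is assumed here. With d = 24/36 = 0.667, the t-test needs 36.31, so 37 per group. Dividing by the Mann-Whitney efficiency 3/π gives 36.31 / 0.955 = 38.02, so 39 per group and 78 in total. The planned size reproduces, and t-test power at 39 per group is 0.828. This point does not depend on the sample size.

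**Step 2. Bias formula.** Let p be the share of hydrocortisone recipients with a contraindication, D their excess hours to shock resolution, and m the mean in everyone else. Suppose the drug has no effect, all such patients are removed from the combination arm, and none from the other:

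- hydrocortisone-alone mean = (1 − p)m + p(m + D) = m + pD
- combination mean = m
- spurious difference = p × D, favouring the combination when D > 0

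For a given p and positive D this is the ceiling. If abstractors find some of these patients on the hydrocortisone-alone side, the bias shrinks. If they find all of them, it vanishes.

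**Step 3. Numbers.** The documents give neither p nor D, so both are assumed. The rejection rate is the power of the two-sided 5% t-test at a shift of p × D, with SD 36 h and 39 per arm (standard error 36 × √(2/39) = 8.15 h).

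| p | D (h) | p × D (h) | Share of 24 h | Rejection rate, no drug effect |
|---|---|---|---|---|
| 5% | 24 | 1.2 | 5% | 0.052 |
| 5% | 48 | 2.4 | 10% | 0.060 |
| 10% | 24 | 2.4 | 10% | 0.060 |
| 10% | 48 | 4.8 | 20% | 0.090 |
| 20% | 24 | 4.8 | 20% | 0.090 |
| 20% | 48 | 9.6 | 40% | 0.214 |

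If 36 h is instead the SD within each subgroup, mixing the subgroups widens the spread in the hydrocortisone-alone arm. By simulation the extreme cell then falls to about 0.19; the others change little.

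**Step 4. Cost of equal application.** To keep 39 per arm after excluding a share p from both arms, 39/(1 − p) must be listed: 39/0.90 = 43.3, so 44 at p = 10%, and 39/0.80 = 48.75, so 49 at p = 20%.

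**The case against.** A reader might infer that the contraindication is checked only on the combination side, and that these patients leave one arm only. The documents do not say so. The criterion stands in the general exclusion list, and the authors restricted a criterion to one arm when they meant to, as the 24-hour rule shows. The Protocol sentence on starting fludrocortisone refers to all the exclusions, including some, such as prior steroid use, that have nothing to do with the tablet. It says when the drug is given, not how the analysis cohort is screened. The missing field is also not decisive: Other Data Collected is not an eligibility checklist, and it likewise lacks a field for initiation by another service or for more than one 100 mg hydrocortisone dose. Abstractors could apply the criterion to hydrocortisone-alone charts. All of this stands, and it is why the point is put as a likely imbalance.

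It does not remove the point. An abstractor on the hydrocortisone-alone side would have to judge, without a definition and knowing the arm, whether a drug that was never due would have been contraindicated. On the combination side the 24-hour and adherence rules remove the same kind of patient without any such judgement. Those two rules are the firmer evidence of one-sided loss.

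The objections to size are also fair. Both p and D are assumed. The criterion accepts a feeding-tube route and the patients are medical, so nothing in the documents supports p as high as 20%. Five of the six cells give a rejection rate of 9% or less. The direction is conditional too: the plan does not say how patients who die before shock resolution enter the primary endpoint, so early deaths in this subgroup could shrink or reverse the bias on that endpoint.

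**Conclusion.** The concern holds as a likely, not certain, differential exclusion. The criterion is general in wording, but the plan offers no procedure or field for applying it to hydrocortisone-alone patients, while two stated rules remove their combination-side counterparts.

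If removal were fully one-sided and affected patients resolved shock more slowly, the primary comparison would be shifted toward the combination by 1.2–9.6 h over the assumed ranges, or 5–40% of the planned difference. The 21% false-positive rate belongs to the most extreme combination only and should not be read as the trial's error rate; at the low end the effect is negligible. The change is worth making because the charts are being reviewed anyway and, without a record by arm, nobody could later show whether the imbalance occurred.

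**What to change.** 1. State that the criterion is judged for every patient on the hydrocortisone list, on both sides, from chart data as of the first hydrocortisone dose, by one written definition and if possible by someone blind to unit side.
2. Add one field: enteral fludrocortisone contraindicated at first hydrocortisone dose, yes or no, with reason. Make this field the only basis for this exclusion.
3. Amend the 24-hour inclusion criterion and the exclusion for therapy not in accordance with assigned group, so that not receiving fludrocortisone does not by itself remove a patient from the primary analysis by assigned side. Without this, step 2 conflicts with both rules.
4. Report the number excluded, with reasons, by arm.

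The cost is one chart field and edits to three eligibility items. Some hydrocortisone-alone patients will be dropped, so about 44 to 49 must be listed per arm to keep 39 if p is 10–20%. Some combination-side patients who did not receive fludrocortisone will stay in the analysis, which may dilute the estimated effect. No dose or treatment rule changes.

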- Continuation of baseline/prior steroid in combination with hydrocortisone/fludrocortisone
- Inhaled corticosteroid use
- Intubation with etomidate
- Amount of diuretics received during study period
- Acute respiratory distress syndrome documented during study period
- Administration of neuromuscular blocker during study period

Statistical Analysis:

Statistical Power

In order to achieve adequate statistical power for the proposed prospective trial, an a priori sample size calculation was completed based on an evidence-based measure of effect size from the APROCCHSS and CORTICUS trials^{3,4}. The evidence-based difference between the treatment groups was 24 hours (Group 1 $M = 96$, $SD = 36$; Group 2 $M = 72$, $SD = 36$), leading to a Cohen's d effect size of 0.67. With a two-tailed hypothesis, an effect size of $d = 0.67$, an alpha value of 0.05, and equal allocation to treatment groups (1:1), 39 participants would be needed for each treatment group. This means the total sample size will be $n = 78$ in order to achieve adequate statistical power for the trial.

Statistical methods

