Frequency and percentage statistics will be used to analyze categorical demographic, predictor, confounding, and outcome variables of interest for the sample. Descriptive statistics will be used to describe the sample characteristics associated with continuous variables. The assumption of normality of continuous distributions will be assessed using skewness and kurtosis statistics. If either statistic is above an absolute value of 2.0, then the distribution will be assumed to be non-normal. Homogeneity of variance between independent groups will be tested using Levene's Test for Equality of Variances. When both statistical assumptions are met, independent samples t-tests will be used to compare the treatment groups on continuous outcomes. Means and standard deviations will be reported and interpreted for these analyses. Mann-Whitney U tests will be used for comparisons when statistical assumptions are violated. Medians and interquartile ranges will be presented and analyzed for non-parametric comparisons. Chi-square tests will be used to test for significant associations between the treatment groups and categorical outcomes. Relative risk with 95% confidence intervals will be reported for significant categorical associations. Multiple regression analysis will be performed with time to resolution of shock as the outcome. Linearity, normality, homoscedasticity, multicollinearity, and autocorrelation assumptions for the regression analysis will be performed. Unstandardized beta coefficients, standard errors of the coefficients, and standardized beta coefficients will be reported and interpreted, along with the change in shared variance (R^2) and respective F-tests. All analyses will be conducted using SPSS Version 22 (Armonk, NY: IBM Corporation) and statistical significance will be assumed at an alpha value of 0.05.

A priori subanalysis will be performed on the following subset of patients: documented history of heart failure and documented chronic kidney disease stage III and IV requiring renal replacement therapy at baseline.

Critical Analysis/Limitations:

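### Treatment follows unit side and calendar period in a fixed order with one swap, but the trial is sized and tested as two independent groups, with no adjustment for side or period specified

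*Combined protocol and SAP*

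**What the plan says.** Under Study Design and Methods the trial is called a "single-center, prospective, open-label, randomized trial". The Protocol section says "Steroid therapy assignments will be randomized based on patient location" and allocates by place and calendar time: "For three consecutive months starting in October 2018, all patients in MCC1 will receive hydrocortisone alone", with the combination on MCC2, and the assignments are exchanged once for the next three months. No random draw of patients, sides or starting order is described. Two reasons are given for the swap: to "account for the difference in number of beds between MCC1 and MCC2" and to "minimize the potential differences in patient acuity by location".

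The Statistical Power section assumes "equal allocation to treatment groups (1:1), 39 participants would be needed for each treatment group". It gives no intracluster correlation, period term or design effect. Under Statistical methods, "independent samples t-tests will be used to compare the treatment groups on continuous outcomes" when assumptions are met, with Mann-Whitney tests otherwise and chi-square tests for categorical outcomes. A multiple regression on time to resolution of shock is also planned, but its predictors are not named and it is not made the primary comparison. The Outcomes and Other Data Collected lists include neither side nor period.

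**The concern.** Treatment is set by the combination of side and period, so the analysis has to account for both. The swap is aimed at differences between sides. It does not balance period if one side supplies more patients, because the larger side puts most of one arm in the first three months and most of the other arm in the second. The protocol itself says that bed numbers differ. Any change between the two periods in case mix, season or practice would then enter the unadjusted treatment difference.

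Clustering is a separate matter. If outcomes vary between the four unit-period cells beyond a constant side effect and a constant period effect, tests that assume independent patients reject too often. At stake are the size of the primary estimate, its p-value, and how far a reader may rely on the word randomized.

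**Working it through.** **Inputs from the plan (Statistical Power).** Means 96 and 72 h (difference 24 h), SD 36 h, two-sided alpha 0.05, 39 per group. Power is not stated.

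**Assumed inputs (not in the plan).** MCC1's patient share s, the period effect P, the intracluster correlation (ICC), and the cluster autocorrelation (CAC: between-period correlation divided by within-period correlation).

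**1. The plan's own figure.** At an assumed 80% power, a t-test with d = 24/36 needs 36.3, so 37 per group. Dividing 36.3 by the Mann-Whitney efficiency 3/π gives 38.02, so 39. The stated 39 is therefore matched by an independent-patient formula. With 39 per group, SE = 36 × √(2/39) = 8.15 h and t-test power is 82.8% (76 df).

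**2. Period imbalance.** With equal volume in both periods, the share of each arm treated in period 2 is s for the combination and 1 − s for hydrocortisone alone. The imbalance is s − (1 − s) = 2s − 1: 0.20 at 60:40 and 0.333 at 2:1. Side is balanced in this case. If instead 45% of patients fall in period 1 and s = 0.6, the cells are:

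| | MCC1 | MCC2 |
|---|---|---|
| Period 1 | 0.27 (alone) | 0.18 (combination) |
| Period 2 | 0.33 (combination) | 0.22 (alone) |

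MCC1's share is 0.33/0.51 = 64.7% of the combination arm and 0.27/0.49 = 55.1% of the other. Side is then unbalanced by 9.6 points and period by 19.8 points.

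**3. Bias and type I error of the unadjusted t-test.** Bias = (2s − 1) × P. The error rate comes from a noncentral t with shift bias/8.15.

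| P (h) | Bias, 60:40 (h) | Type I error | Bias, 2:1 (h) | Type I error |
|---|---|---|---|---|
| 6 | 1.2 | 5.2% | 2 | 5.7% |
| 12 | 2.4 | 6.0% | 4 | 7.7% |
| 24 | 4.8 | 9.0% | 8 | 16.3% |

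These rates hold the SD at 36 h. If the period effect also widens the within-arm spread, by s(1 − s)P² in variance, the 24 h rates fall to about 7.4% and 14.0%.

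**4. Cost of adjustment.** Variance rises by 1/(1 − (2s − 1)²): 1/(1 − 0.04) = 1.042 at 60:40 and 1/(1 − 0.111) = 1.125 at 2:1. Power with 78 patients (74 df) is 81.2% and 78.2%, before any gain from severity covariates.

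**5. Clustering.** Design effect = 1 + (m − 1) × ICC − m × ICC × CAC, with m = 78/4 = 19.5 patients per cell.

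| ICC | CAC | Design effect | Type I error, planned test | Power, planned test | Power, corrected SE |
|---|---|---|---|---|---|
| 0.02 | 1 | 0.98 | 4.8% | 83.0% | 83.6% |
| 0.05 | 1 | 0.95 | 4.5% | 83.4% | 84.7% |
| 0.02 | 0.8 | 1.058 | 5.7% | 82.1% | 80.7% |
| 0.05 | 0.8 | 1.145 | 6.7% | 81.2% | 77.5% |
| 0.02 | 0.5 | 1.175 | 7.0% | 80.9% | 76.5% |
| 0.05 | 0.5 | 1.438 | 10.1% | 78.6% | 67.9% |

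**6. What adjustment cannot do.** An intercept plus treatment, side and period makes four parameters for four cell means. The fit is exact, so no degrees of freedom remain for variation between cells, and the treatment contrast is the side-by-period interaction. In simulation (cells of 23/16/23/16 or 26/13/26/13), the model with side and period has type I error 5.0% at CAC 1 and about 5.8% to 10.7% at CAC 0.8 to 0.5.

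**The case against.** The strongest reply is that the swap already deals with stable differences between sides, and the CAC 1 rows above bear this out: there is no inflation. The regression could also include side and period. Both could probably be recovered, because the exclusion for treatment that does not match the assigned location requires side to be known, and arm plus side determines period.

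Every driver of the size is assumed. At 60:40, period effects of 6 to 12 h take the type I error only to 5.2–6.0%. The largest figures need a period effect as big as the whole hypothesised treatment effect. At ICC 0.01 the planned test's simulated error is only 5.4–6.1% at CAC 0.8 to 0.5. On mean squared error, adjustment pays only when P exceeds about 8.3 h (60:40) or 8.6 h (2:1), before severity covariates, and it does nothing for cell-level variation. Silence about how the order was chosen does not prove that there was no draw.

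Much of this stands as a limit on the likely harm. It does not close the gap. Predictors left unnamed can be omitted or chosen after the data are seen, and the swap does not balance period when the sides differ in size. The protocol describes no chance mechanism, and even a coin toss between two sequences would not justify an analysis as if patients had been randomised individually. The point that a linear model needs a stated fallback for skewed data is fair and is taken up in the fix.

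**Conclusion.** The concern holds and should be corrected before outcomes are examined. The mismatch between the allocation and the analysis is certain from the text; the size of the harm is not.

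The removable part is the period imbalance of 2s − 1. It is small for modest period effects and material for large ones: type I error about 5.2% to 9.0% at 60:40 and 5.7% to 16% at 2:1, for period effects of 6 to 24 h. This rests on assumed shares and period effects, roughly normal data, equal volume in both periods, and an SD of 36 h.

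The part that cannot be removed is variation specific to one side in one period. It is nil at CAC 1. At ICC 0.02–0.05 and CAC 0.8–0.5 it gives the planned test a type I error of about 5.7% to 10.1%. With four cells it cannot be estimated from the trial's own data, so it limits what the trial can conclude.

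**What to change.** - Describe the design as a cluster crossover with two units, two periods and a fixed order, not as randomized. If the starting order was drawn by chance, say how.
- Record MCC side and period explicitly for every patient.
- Make the primary comparison a model with treatment, side and period as fixed effects, plus prespecified baseline severity: vasopressor dose at steroid start, and SOFA with its time point stated (the data list gives none). State in advance how the adjusted analysis will handle skewed times, since the Mann-Whitney fallback as written carries neither side nor period.
- Adjust secondary outcomes in the same way, using regression in place of chi-square tests where event counts allow.
- Restate power with the factor 1/(1 − (2s − 1)²), using the expected patient shares, and over a range of ICC and CAC that includes CAC 1.
- State as a limitation that, with four unit-period cells, treatment cannot be separated from side-specific time trends, that between-cell variance cannot be estimated, and that adjustment does not remove this error.

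The cost is two recorded fields and two model terms; the severity covariates are already collected and no patients are added. The price is some precision: variance higher by a factor of 1.04 at 60:40 or 1.125 at 2:1, and power of about 81% or 78% instead of 82.8%, before any gain from the severity covariates.
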